# 3.6.3 Blinding

The present trial is double-blind. The subject, the investigator and other trial staff at the site will be blinded to treatment allocation during the conduct of the trial. Blinding is achieved by randomizing subjects in a 1:1:1:1 ratio to a vaginal ring containing quinagolide dose load 360  $\mu$ g, 720  $\mu$ g and 1080  $\mu$ g or placebo, all of which are identical in appearance, flexibility and softness.

Similarly, the Ferring clinical team (e.g. data manager, statistician, clinical trial manager, clinical project leader, medical writer, pharmacovigilance physician, pharmacovigilance manager and medical officer) will be blinded to treatment allocation until breaking of the blind. The blind will be broken when the trial database is declared clean and is released to the responsible statistician.

As described in section 3.5, an external DMC will have access to unblinded interim data presented by treatment group and, if needed, unblinded safety data of some subjects presented also by treatment group. In any case, the DMC will keep the data and analyses confidential from the Ferring clinical team.

Since the primary endpoint and the secondary efficacy endpoints in this trial are based on PRO measures, precaution must be taken to ensure the blinding of subjects to treatment allocation throughout the trial. To avoid potential speculation of treatment allocation by comparing current pain scores against previous scores, subjects are not given any access to historically reported data after having submitted their answers in the e-Diary. Investigators, trial site staff and Ferring clinical team will also be blinded to the results of some laboratory parameters potentially linked to quinagolide's mechanism of action. In addition, all subjects will be asked at the end of treatment which treatment (quinagolide or placebo) they believe they have received to evaluate the risk of inadvertent unblinding. These practices are in line with FDA PRO guidance.

[figure not shown]
#### 3.6.4 Selection of Doses in the Trial

In a dose-response trial it is desirable to test a relatively wide span of doses to identify the most appropriate dose(s) for future trials. The dose selection should also ensure that it is possible to discern clinically meaningful differences within a span that is acceptable with respect to subject safety.

Selection of doses in this trial is based on safety, tolerability and PK obtained from phase 1 trials. Oral administration of quinagolide at doses up to 75  $\mu$ g once daily for 18-20 weeks appeared to reduce the size of lesions in endometriosis patients. In the first phase 1 trial (000076), after repeated oral administration of 75  $\mu$ g quinagolide tablets once daily for 5 days, the mean Cmax was 8 pg/mL, the steady-state trough level was 0.8 pg/mL, and AUCtau was 42.3 h\*pg/mL. The corresponding values after intravaginal administration of 75  $\mu$ g tablets was 13 pg/mL, 7 pg/mL and 225 h\*pg/mL, respectively, which was 1.6-fold, 8-fold and 5-fold higher than after oral administration, demonstrating that intravaginal administration circumvents the first pass metabolism. It also showed that intravaginal administration compared with oral administration (Tmax about 1 hour). Although intravaginal administration of quinagolide tablets up to 75  $\mu$ g was associated with higher exposure, it was well tolerated with lower incidences of treatment-related adverse events, compared with oral administration.

In the subsequent trial (000155), quinagolide vaginal ring at a target release rate of quinagolide 4.5  $\mu$ g/day, 9  $\mu$ g/day and 13.5  $\mu$ g/day were investigated. The plasma concentration of quinagolide increased initially in approximate proportionality. Following the initial peak, the plasma concentration declined slowly over the treatment period and the trough levels were maintained between 1-10 pg/mL for all three doses for up to 35 days. The median Tmax following administration of quinagolide vaginal rings was approximately 36-48 hours for all three doses.

Selection of the doses in the present trial is based on the PK profiles obtained from these two phase 1 trials, which are illustrated in Figure 3-2 showing the mean observed PK parameters of the 75  $\mu$ g oral and intravaginal tablets during a daily dosing interval extended to 28 days, compared to the PK profiles of quinagolide vaginal rings administered for 28 days. For the highest dose of quinagolide vaginal ring, the mean Cmax of 10.9 pg/mL does not exceed the mean Cmax of 13 pg/mL observed with the 75  $\mu$ g intravaginal tablet. Following the initial peak, the concentration is similar to the mean Cmax of 8 pg/mL observed with the 75  $\mu$ g oral tablet. For the lowest dose of quinagolide vaginal ring, the mean concentration of quinagolide at day 28 resembles the steady state trough of 0.8 pg/mL observed with the 75  $\mu$ g oral tablet. Therefore, for the three proposed doses of quinagolide vaginal ring, the maximum concentrations are below the maximum concentration of the 75  $\mu$ g intravaginal tablet and the concentrations after the initial peak are within the concentration range of the 75  $\mu$ g oral tablet.

Abbreviations: Conc=concentration, QVR=quinagolide vaginal ring

#### Figure 3-2 Dose Selection for Quinagolide Vaginal Ring

The proposed three doses provide a dose span with an equal absolute dose difference (i.e. a target release rate difference of 4.5  $\mu$ g/day) to investigate the treatment effect of quinagolide. The outcome of the present trial should allow subsequent examination of the dose-response curve and to identify the dose(s) for quinagolide vaginal ring to be used in future trials.

The doses for the rescue analgesic medications used during this trial are in line with the recommendations in the respective product' labelling for the indication of pain relief.

# 3.6.5 Selection and Timing of Dose for Each Subject

In this clinical trial, the duration of treatment is based on individual subject's menstrual cycle length rather than calendar time points, matching the visits and timings of evaluation with the replacement of the vaginal ring. A menstrual cycle is considered the period between day 7 of return of menses (RM+7) in a cycle until the following day 7 of return of menses of the next cycle. Visits on RM+7 can be scheduled day 6 to day 10 day of return of menses (RM+6-10).

Subjects will be instructed to insert the assigned ring in the upper part of the vagina at RM+7 visits, a timing that corresponds to the stop of menstrual bleeding and is convenient for administration of a vaginal product, which can therefore easily be remembered and followed by subjects. The vaginal ring will be kept in the vagina continuously for one menstrual cycle until being replaced by the next

ring on RM+7 of the next cycle when the subject visits the clinic. Thus, quinagolide will be given sufficient time to inhibit the endometriotic lesions prior to return of the menses in the next cycle, when the majority of the most severe endometriosis-related pain occurs.

# **3.6.6** Selection of the Trial Population

The trial population consists of surgically confirmed endometriosis patients commonly included in clinical trials. After surgical treatment of endometriosis, these subjects still have recurrence of symptoms and moderate to severe endometriosis-related pain. Confirmation of endometriosis by laparoscopy or laparotomy is considered to be the gold standard for the diagnosis of the disease. It is increasingly recognized that ultrasound evidence of endometrioma, combined with recurrent endometriosis-related pain, is a useful clinical diagnostic measure of endometriosis and can identify endometriosis with high accuracy.

Moderate to severe endometriosis pain for this trial is defined as having a mean daily NRS score of  $\geq$ 4 for the worst endometriosis-related pain during each run-in menstrual cycle. The cut-off of 4 is the most commonly recommended lower limit for moderate pain on NRS. Results of some other endometriosis studies were also taken into consideration in choosing this cut-off. In two recently completed pivotal phase 3 trials among 1689 endometriosis patients, a mean daily NRS score of approximately 5.5 was recorded for endometriosis pain at its worst during a baseline period of 35 days. In an observational study for a minimum of 12 weeks, the 268 subjects reported a mean daily NRS score of 3.61 for endometriosis-related pain at its worst as well as a daily NRS score of  $\geq$ 7 for at least 4 days.

The trial will include pre-menopausal women  $\geq 18$  years without an upper age limit and will thereby cover the age span of most endometriosis patients.

The exclusion criteria incorporate the contraindications for the use of dopamine agonists and rescue analgesics.

# 3.6.7 Discontinuation Criteria (Stopping and Withdrawal Criteria)

The discontinuation criteria consist of criteria for discontinuation from treatment (stopping criteria) and criteria for discontinuation from trial (withdrawal criteria). For any premature discontinuation, an end-of-treatment visit (section 6.4.6) should be scheduled as soon as possible (preferably within 7 days of the last ring removal) and the investigator will obtain all the required details and document the date and the main reason of premature discontinuation in the electronic case report form (e-CRF).

#### **Stopping Criteria (Discontinuation from Treatment)**

#### Stopping Criteria on Subject Level

Subjects will be discontinued from the treatment if any of the following stopping criteria are met:

- Any significant changes in valvular regurgitation or stenosis from baseline associated with clinical signs and symptoms
- Any clinically significant abnormal ECG finding defined as prolongation of QTcF ≥500 msec or change from baseline QTcF value of ≥60 msec confirmed by the central cardiac laboratory
- Treatment-related syncope (orthostatic collapse associated with an abrupt, transient, complete loss of consciousness and inability to maintain postural tone, with rapid and spontaneous recovery) incompatible with continuing treatment
- Treatment-related alteration in consciousness or mental status (such as confusion, amnesia, loss of alertness and disorientation) incompatible with continuing treatment
- Treatment-related pathological behaviors of impulse control disorders including pathological gambling, compulsive buying, binge eating, and hypersexuality (see section 7.2.2.10) incompatible with continuing treatment
- Treatment-related acute psychosis, e.g. hallucinations/delusion

#### Stopping Criteria on Trial Level

The DMC will consider the following SAEs for stopping or modifying the trial (i.e. discontinuing one dose, several doses or the trial):

- One subject discontinued due to a diagnosis of cardiac valvulopathy confirmed by an independent cardiologist (see section 7.2.2.9)
- More than three subjects discontinued due to treatment-related syncope (orthostatic collapse associated with an abrupt, transient, complete loss of consciousness and inability to maintain postural tone, with rapid and spontaneous recovery)
- More than three subjects discontinued due to treatment-related significant alteration in consciousness or mental status (such as confusion, amnesia, loss of alertness and disorientation)

The DMC will be requested to access the unblinded safety data presented by treatment group and will recommend whether one dose, several doses or the trial should be discontinued based on the results of the analysis.

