# 6.4.6 Visit 10 (End-of-Treatment / RM+7 of Cycle 4)

If subjects attend all scheduled visits and complete the treatment, an end-of-treatment visit (visit 10) will be scheduled on RM+6-10 of cycle 4. If subjects are discontinued from the treatment prematurely, an end-of-treatment visit with the following end-of-treatment assessments should be scheduled as soon as possible (preferably within 7 days of the last ring removal).

The following must take place first:

- Ensure the completion of the EHP-30 questionnaire by the subject
- Ensure the completion of the PGIS scale by the subject

- Ensure the completion of the PGIC scale by the subject
- Completing the first part of B&B scale based on the subject's verbal response
- Completing the questionnaire for impulsive-compulsive disorders (QICD) based on the subject's verbal responses
- Ensure the completion of the eC-SSRS by the subject

Once the above has been completed, the following must be performed:

- Vital signs [note: vital signs must be performed before blood sampling]
- ECG [*note*: this can be done within ±2 weeks of the visit and must be performed before blood sampling when applicable]
- Echocardiography [*note*: this can be done within ±2 weeks of the visit]
- Physical examination
- Gynecological examination
- Transvaginal ultrasound
- Investigator completing the second part of B&B scale based on findings from an examination of pelvic tenderness and induration (see section 7.2.2.1)
- Urine pregnancy test [*note*: this is performed prior to ring insertion / removal. Results must be negative. If positive, a serum test must be done]
- Urinalysis
- Blood collection for analysis of:
  - Plasma concentration of quinagolide and metabolites [*note*: this is performed prior to ring insertion / removal]
  - Clinical chemistry and hematology parameters
- Removal of the used ring. Supervision by the site staff can be provided if needed
- Ensure the completion of the ring acceptability questionnaire (full version) by the subject

Lastly, the following must take place at this visit:

- e-Diary review
- Confirmation of the start date and, if applicable, stop date of menses in the current cycle
- Drug accountability of the ring and ibuprofen as applicable
- Recording of use of any concomitant medications
- Recording of adverse events
- Completion the end-of-treatment question where subjects will be asked which treatment (placebo or quinagolide) they believe they have received

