## 7.2.2.9 Echocardiography

Echocardiography will be performed within cycle -1 and at cycle 4 (around visits 3 and 10). Echocardiography at screening can be arranged anytime during cycle -1, e.g. at LH+7 visit (visit 3) but results must be available prior to randomization. The report must be reviewed, signed and dated by the investigator before randomization. Echocardiography at cycle 4 can be performed within  $\pm 2$  weeks of visit 10.

The 2-dimensional (2D) echocardiography and Doppler echocardiography will be used for assessment of valvular structure and function with a calibrated echocardiography device. For the same subject, all echocardiography assessments in this trial should be performed by the same type of echocardiography device at the same center.

Quinagolide, FE 999051 Vaginal Delivery System Clinical Trial Protocol

After the subject has been in supine position for at least 5 minutes, the structure of mitral, tricuspid, aortic and pulmonary valves will be assessed semi-qualitatively by 2D echocardiography. Valvular regurgitation will be assessed by Doppler echocardiography. All echocardiography video clips at each visit will be sent to a central cardiac laboratory and stored for potential further evaluation. Assessment performed prior to randomization will be used as baseline and will be compared against assessments performed at cycle 4.

The echocardiography technicians and board-certified cardiologists from the central cardiac laboratory will evaluate each assessment as normal or abnormal according to American College of Cardiology / American Heart Association guidelines for valvular heart disease. If abnormal, the level of valvular regurgitation and valvular stenosis will be specified as mild, moderate or severe and valvular structure will be evaluated as well. Criteria are provided in a separate manual.

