At cycle 4, any changes from baseline will be assessed by the primary cardiologist(s) at the central cardiac laboratory as significant or not significant. In case of significant change from baseline, irrespective of the change level, the echocardiogram will be re-evaluated and confirmed by a secondary cardiologist at the central cardiac laboratory. The degree of change in valve stenosis or regurgitation will be confirmed by quantitative analysis of gradients and valve area for stenotic lesions and by vena contracta width, jet area, and Doppler waveforms for regurgitant lesions. If the change is confirmed to be significant by the secondary cardiologist, the finding should be reported to the investigator who should evaluate the clinical significance of the finding in relation with clinical symptoms and other tests (e.g. ECG and vital signs). The subject will be discontinued from the treatment (see section 3.6.7) and will be referred to a cardiologist for further follow-up. A repeated echocardiography will be required and all video clips saved previously for the discontinued subject will be further evaluated by an external cardiologist for an independent evaluation of the findings and for a potential diagnosis of cardiac valvulopathy.

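### In protocol version 6.0 the one-case valvulopathy trigger for unblinded DMC review, read literally, misses a case confirmed after treatment was completed or was stopped for another reason

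*Protocol*

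**What the plan says.** Protocol section 3.6.7 introduces the trial-level criteria with "The DMC will consider the following SAEs for stopping or modifying the trial". The first of three items is "One subject discontinued due to a diagnosis of cardiac valvulopathy confirmed by an independent cardiologist", with a cross-reference to section 7.2.2.9. These criteria stand under the heading for discontinuation from treatment. Withdrawal from the trial has a separate list, which names no valve finding and otherwise leaves withdrawal to the woman or to the investigator's discretion.

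Sections 3.5 and 3.6.7 make the DMC's access to unblinded safety data by treatment group follow from these criteria being met. The internal Clinical Monitoring Committee (section 3.4) sees blinded data only.

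Sections 6.4.6 and 7.2.2.9 schedule one echocardiogram in cycle -1 and one around visit 10, with a window of two weeks either side. Visit 10 includes "Removal of the used ring. Supervision by the site staff can be provided if needed". A woman who stops early has the same end-of-treatment assessments, preferably within 7 days of her last ring coming out.

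Once a second central cardiologist confirms a significant change, section 7.2.2.9 says: "The subject will be discontinued from the treatment (see section 3.6.7) and will be referred to a cardiologist for further follow-up". A repeat scan follows, and "all video clips saved previously for the discontinued subject will be further evaluated by an external cardiologist", with a view to a possible diagnosis of valvulopathy. Sections 3.6.7 and 7.4.20 record a reason for stopping only for women who did not complete treatment; section 3.6.7 asks for one main reason.

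**The concern.** The trigger depends on why a woman stopped treatment, while the scan that would reveal the problem is scheduled for when treatment ends. A woman who has completed four cycles has no treatment left to discontinue. A woman who stopped for another reason already has that reason on her form. In either case an independently confirmed valvulopathy could exist without meeting the criterion that calls for unblinded review.

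The threshold is a single case, so the wording decides whether that case counts. Enrolment is staggered, so other women may be wearing active rings when an earlier participant has her end-of-treatment scan. Whether one dose, several doses or the whole trial should stop is the question that review by dose group is meant to answer.

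**Working it through.** The plan gives no operating characteristic for this trigger, so there is no figure to reproduce. The check is to follow each route to a diagnosis and ask whether it meets the words of the criterion.

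| Situation under version 6.0 | Is there treatment to discontinue because of the finding? | Literal trigger |
|---|---|---|
| Scan in the 14 days before visit 10, read twice and acted on before ring removal | Yes | Can be met |
| Scan before visit 10, change confirmed only afterwards | No | Not met |
| Scan at visit 10 after ring removal, or in the following 14 days | No | Not met |
| Woman stopped early for another reason, then scanned | No; main reason already fixed | Not met |
| Unscheduled scan during treatment, for example for symptoms | Yes | Can be met |

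Timing, from sections 6.4.6 and 7.2.2.9:
- Completer: ring out at visit 10, scan up to 14 days later.
- Early stopper seen at the preferred limit: 7 + 14 = 21 days after the last ring.
- Scheduled scans after baseline and before the end-of-treatment window: 0.

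Section 7.2.2.9 adds a second difficulty. It puts discontinuation before the external reading and words that reading for a discontinued subject. For a completer, a literal reader could conclude that the independent confirmation required by the trigger is never requested. An early stopper is a discontinued subject, so the reading can reach her, but the diagnosis is still not why she stopped.

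Protocol version. The SAP (sections 1 and 3) says that versions 4.0 and 5.0 had Part A (cycles 1 to 4) and Part B (cycles 5 to 8), with echocardiograms at cycles 4 and 8. The cycle 4 scan then preceded four more cycles, so discontinuation because of it was possible. If the trigger was worded the same way (those versions were not supplied), the gap applied mainly at the cycle 8 scan. Version 6.0 removed Part B and so moved the cycle 4 scan to the end of treatment.

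Scale. Planned evaluable women at end of treatment are 208/280 = 74% of those randomized, and 70 x 3 = 210 women are planned for active rings. These count women, not cases, and do not measure the gap.

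Purely as an illustration, let p be an assumed valvulopathy rate on active rings and f an assumed share of cases that become discontinuations due to the diagnosis. The chance that at least one case meets the trigger is 1 - (1 - p x f)^210:

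| p | f = 1 | f = 0.5 | f = 0.25 | f = 0.1 |
|---|---|---|---|---|
| 0.5% | 0.651 | 0.409 | 0.231 | 0.100 |
| 1% | 0.879 | 0.651 | 0.409 | 0.190 |
| 2% | 0.986 | 0.879 | 0.651 | 0.343 |

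Neither p nor f comes from the documents. The table shows only that a one-case trigger is sensitive to which cases qualify.

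**The case against.** The best reply is that the criterion should be read with the section it cites. Section 7.2.2.9 is written for the cycle 4 scan and leads from a confirmed change to the external cardiologist's opinion, so the end-of-treatment scan was evidently meant to feed the trigger. That stands as evidence of intent. It does not alter the condition in the criterion, and its own instruction to discontinue cannot be carried out for a woman who has finished.

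The DMC charter may also settle the matter. It was not supplied, so this remains open.

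Other safeguards exist. A clinically significant echocardiography finding is an adverse event (section 8.1). Serious events are reported within 24 hours (section 8.5.2), and related ones found after the last visit must also be reported (section 8.6.2). Section 5.5.2 allows individual unblinding for a suspected unexpected serious reaction. Section 1.3 reports no valvular heart disease with quinagolide, so a serious case judged related could well take that route. A reader might therefore infer from this point that a case would go unnoticed or stay blinded; the documents do not support that. What none of these steps does by itself is ask the DMC to review safety by dose group.

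Two other strong readings also fail. One is that no completer could ever meet the trigger: half the scan window lies before visit 10, and an unscheduled scan is possible. The other is that the gap affected the whole trial from 2018: the SAP says most women were randomized under version 5.0, where the cycle 4 scan came mid-treatment.

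**Conclusion.** The point holds as a wording defect in version 6.0 that should be corrected. Two groups fall outside the literal trigger: women whose valvulopathy is confirmed after they completed treatment, and women who had already stopped for another reason. The effect in missed cases cannot be quantified, because the documents give no incidence, no central reading time and no share of scans done before visit 10.

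The conclusion rests on reading the criterion as discontinuation from treatment, as its heading indicates, and on the charter not already counting such cases. Confidence is medium for the second reason. The protocol expects the risk to be low. The SAP records that the trial ended early, so this concerns the plan as written and not any event known to have been missed.

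**What to change.** In section 3.6.7, reword the first trial-level item to: *One subject in whom an independent cardiologist confirms cardiac valvulopathy, where the finding was made after first ring insertion and up to the end-of-trial visit (including follow-up of the end-of-treatment echocardiogram), whether or not treatment was discontinued because of it.* Change the lead-in from SAEs to events only if non-serious confirmed cases are meant to count; that is a separate decision for the sponsor. Leave the syncope and altered-consciousness items unchanged.

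In section 7.2.2.9, apply the repeat echocardiogram and external cardiologist review to every significant change that the secondary cardiologist confirms, and require discontinuation only if treatment is still ongoing. Align the DMC charter if it differs.

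No scheduled visit or scan is added. The cost is the amended wording, plus a rare extra repeat scan, external reading or DMC review.
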